SOURCE: MMRMOUT; TABLE: statlab.lis; RUN: 31AUG2020 08:32; ANALYSIS DATASET CREATED: 16JUN2020 08:14
 PROGRAM: /opt/sas/Data/DAP/EB1020/P40520100014/STAT/Program.dev/DOC_STAT/stat1.sas
 OPDC, NEW DRUG APPLICATION, IND # 119,361 CENTANAFADINE STAT-4.1.2 FINAL

CENTANAFADINE
PROTOCOL 405-201-00014

1 OF 6

STAT-4.2
Proc GLM Output for Change from Baseline to Day 42 in AISRS Total Score, LOCF
(Efficacy Sample)

----- Parameter Code=AI SRSTOT Analysis Visit (N)=42 -----

The GLM Procedure
Class Level Information

Class	Levels	Values
TRTPN	3	1 2 3
POOLCNTR	39	

Number of Observations Read	421
Number of Observations Used	421

SOURCE: GLMOUT; TABLE: stat1b.lis; RUN: 31AUG2020 08:32; ANALYSIS DATASET CREATED: 16JUN2020 08:14
PROGRAM: /opt/sas/Data/DAP/EB1020/P40520100014/STAT/Program.dev/DOC_STAT/stat1.sas
OPDC, NEW DRUG APPLICATION, IND # 119,361 CENTANAFADINE STAT-4.2 FINAL

CENTANAFADINE
 PROTOCOL 405-201-00014

2 OF 6

STAT-4.2
 Proc GLM Output for Change from Baseline to Day 42 in AISRS Total Score, LOCF
 (Efficacy Sample)

 ----- Parameter Code=AISRSTOT Analysis Visit (N)=42 -----

The GLM Procedure

Dependent Variable: CHG Change from Baseline

Source	DF	Sum of Squares	Mean Square	F Value	Pr > F
Model	41	8805.99497	214.78037	2.07	0.0002
Error	379	39250.45633	103.56321		
Corrected Total	420	48056.45131			

R-Square Coeff Var Root MSE CHG Mean
 0.183243 -105.7081 10.17660 -9.627078

Source	DF	Type III SS	Mean Square	F Value	Pr > F
TRTPN	2	1454.328052	727.164026	7.02	0.0010
POOLCNTR	38	6862.153762	180.582994	1.74	0.0053
BASE	1	280.694601	280.694601	2.71	0.1005

SOURCE: GLMOUT; TABLE: stat1b.lis; RUN: 31AUG2020 08:32; ANALYSIS DATASET CREATED: 16JUN2020 08:14
 PROGRAM: /opt/sas/Data/DAP/EB1020/P40520100014/STAT/Program.dev/DOC_STAT/stat1.sas
 OPDC, NEW DRUG APPLICATION, IND # 119,361 CENTANAFADINE STAT-4.2 FINAL

CENTANAFADINE
 PROTOCOL 405-201-00014

3 OF 6

STAT-4.2
 Proc GLM Output for Change from Baseline to Day 42 in AISRS Total Score, LOCF
 (Efficacy Sample)

 ----- Parameter Code=AI SRSTOT Analysis Visit (N)=42 -----

The GLM Procedure

Level of TRTPN	N	-----CHG-----		-----BASE-----	
		Mean	Std Dev	Mean	Std Dev
1	140	-10.7071429	10.8359224	37.5857143	6.75041775
2	140	-11.0571429	10.7125768	38.7642857	6.95578090
3	141	-7.1347518	10.1624096	37.6453901	6.34837972

SOURCE: GLMOUT; TABLE: stat1b.lis; RUN: 31AUG2020 08:32; ANALYSIS DATASET CREATED: 16JUN2020 08:14
 PROGRAM: /opt/sas/Data/DAP/EB1020/P40520100014/STAT/Program.dev/DOC_STAT/stat1.sas

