 PROGRAM: /opt/sas/Data/DAP/EB1020/P40520100014/STAT/Program.dev/DOC_STAT/stat1.sas
 OPDC, NEW DRUG APPLICATION, IND # 119,361 CENTANAFADINE STAT-4.2 FINAL

CENTANAFADINE
 PROTOCOL 405-201-00014

1 OF 6

STAT-4.3
 Proc GLM Output for Change from Baseline to Day 42 in AISRS Total Score, OC
 (Efficacy Sample)

 ----- Parameter Code=AI SRSTOT Analysis Visit (N)=42 -----

The GLM Procedure

Class Level Information

Class	Levels	Values
TRTPN	3	1 2 3

Number of Observations Read	421
Number of Observations Used	421

SOURCE: GLMOUT; TABLE: stat1c.lis; RUN: 31AUG2020 08:32; ANALYSIS DATASET CREATED: 16JUN2020 08:14
 PROGRAM: /opt/sas/Data/DAP/EB1020/P40520100014/STAT/Program.dev/DOC_STAT/stat1.sas
 OPDC, NEW DRUG APPLICATION, IND # 119,361 CENTANAFADINE STAT-4.3 FINAL

CENTANAFADINE
 PROTOCOL 405-201-00014

2 OF 6

STAT-4.3
 Proc GLM Output for Change from Baseline to Day 42 in AISRS Total Score, OC
 (Efficacy Sample)

 ----- Parameter Code=AISRSTOT Analysis Visit (N)=42 -----

The GLM Procedure

Dependent Variable: CHG Change from Baseline

Source	DF	Sum of Squares	Mean Square	F Value	Pr > F
Model	3	1943.84121	647.94707	5.86	0.0006
Error	417	46112.61010	110.58180		
Corrected Total	420	48056.45131			

R-Square Coeff Var Root MSE CHG Mean
 0.040449 -109.2314 10.51579 -9.627078

Source	DF	Type III SS	Mean Square	F Value	Pr > F
TRTPN	2	1249.405044	624.702522	5.65	0.0038
BASE	1	618.365333	618.365333	5.59	0.0185

SOURCE: GLMOUT; TABLE: stat1c.lis; RUN: 31AUG2020 08:32; ANALYSIS DATASET CREATED: 16JUN2020 08:14
 PROGRAM: /opt/sas/Data/DAP/EB1020/P40520100014/STAT/Program.dev/DOC_STAT/stat1.sas
 OPDC, NEW DRUG APPLICATION, IND # 119,361 CENTANAFADINE STAT-4.3 FINAL

Until the information herein is released by Otsuka to the public domain, the contents of this document are Otsuka confidential information and should not be duplicated or re-distributed without prior written consent of Otsuka.

CENTANAFADINE
 PROTOCOL 405-201-00014

3 OF 6

STAT-4.3
 Proc GLM Output for Change from Baseline to Day 42 in AISRS Total Score, OC
 (Efficacy Sample)

 ----- Parameter Code= AISRSTOT Analysis Visit (N)=42 -----

The GLM Procedure

Level of TRTPN	N	-----CHG-----		-----BASE-----	
		Mean	Std Dev	Mean	Std Dev
1	140	-10.7071429	10.8359224	37.5857143	6.75041775
2	140	-11.0571429	10.7125768	38.7642857	6.95578090
3	141	-7.1347518	10.1624096	37.6453901	6.34837972

SOURCE: GLMOUT; TABLE: stat1c.lis; RUN: 31AUG2020 08:32; ANALYSIS DATASET CREATED: 16JUN2020 08:14

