 PROGRAM: /opt/sas/Data/DAP/EB1020/P40520100014/STAT/Program.dev/DOC_STAT/stat1.sas
 OPDC, NEW DRUG APPLICATION, IND # 119,361 CENTANAFADINE STAT-4.6 FINAL

CENTANAFADINE
 PROTOCOL 405-201-00014

9 OF 24

STAT-4.6
 Unadjusted Mean Change from Baseline to Double Blind Tretmnet Period by Study Day in AISRS Total Score, LOCF
 (Efficacy Sample)

 ----- Analysis Visit (N)=35 -----

The TTEST Procedure

Variable: CHG (Change from Baseline)

TRTPN	N	Mean	Std Dev	Std Err	Minimum	Maximum
1	140	-10.2929	10.6376	0.8990	-51.0000	11.0000
3	141	-6.9716	9.5086	0.8008	-37.0000	12.0000
Diff (1-2)		-3.3212	10.0869	1.2035		

TRTPN	Method	Mean	95% CL Mean	Std Dev	95% CL Std Dev
1		-10.2929	-12.0704 -8.5153	10.6376	9.5206 12.0539
3		-6.9716	-8.5548 -5.3885	9.5086	8.5133 10.7695
Diff (1-2)	Pooled	-3.3212	-5.6903 -0.9522	10.0869	9.3149 10.9995
Diff (1-2)	Satterthwaite	-3.3212	-5.6914 -0.9511		

Method	Variances	DF	t Value	Pr > t
Pooled	Equal	279	-2.76	0.0062
Satterthwaite	Unequal	275.12	-2.76	0.0062

SOURCE: TTESTLOCF; TABLE: stat1h.lis; RUN: 31AUG2020 08:32; ANALYSIS DATASET CREATED: 16JUN2020 08:14
 PROGRAM: /opt/sas/Data/DAP/EB1020/P40520100014/STAT/Program.dev/DOC_STAT/stat1.sas
 OPDC, NEW DRUG APPLICATION, IND # 119,361 CENTANAFADINE STAT-4.6 FINAL

CENTANAFADINE
 PROTOCOL 405-201-00014

10 OF 24

STAT-4.6

Unadjusted Mean Change from Baseline to Double Blind Treatment Period by Study Day in AISRS Total Score, LOCF
 (Efficacy Sample)

 ----- Analysis Visit (N)=35 -----

The TTEST Procedure

Variable: CHG (Change from Baseline)

Equality of Variances

Method	Num DF	Den DF	F Value	Pr > F
Folded F	139	140	1.25	0.1862

SOURCE: TTESTLOCF; TABLE: stat1h.lis; RUN: 31AUG2020 08:32; ANALYSIS DATASET CREATED: 16JUN2020 08:14
 PROGRAM: /opt/sas/Data/DAP/EB1020/P40520100014/STAT/Program.dev/DOC_STAT/stat1.sas
 OPDC, NEW DRUG APPLICATION, IND # 119,361 CENTANAFADINE STAT-4.6 FINAL

CENTANAFADINE
 PROTOCOL 405-201-00014

11 OF 24

STAT-4.6
 Unadjusted Mean Change from Baseline to Double Blind Tretmnet Period by Study Day in AISRS Total Score, LOCF
 (Efficacy Sample)

 ----- Analysis Visit (N)=42 -----

The TTEST Procedure

Variable: CHG (Change from Baseline)

TRTPN	N	Mean	Std Dev	Std Err	Minimum	Maximum
1	140	-10.7071	10.8359	0.9158	-51.0000	11.0000
3	141	-7.1348	10.1624	0.8558	-39.0000	12.0000
Diff (1-2)		-3.5724	10.5034	1.2532		

TRTPN	Method	Mean	95% CL Mean	Std Dev	95% CL Std Dev
1		-10.7071	-12.5178 -8.8964	10.8359	9.6981 12.2787
3		-7.1348	-8.8268 -5.4427	10.1624	9.0987 11.5100

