 PROGRAM: /opt/sas/Data/DAP/EB1020/P40520100014/STAT/Program.dev/DOC_STAT/stat1.sas
 OPDC, NEW DRUG APPLICATION, IND # 119,361 CENTANAFADINE STAT-4.7 FINAL

CENTANAFADINE
 PROTOCOL 405-201-00014

11 OF 24

STAT-4.7
 Unadjusted Mean Change from Baseline to Double Blind Tretmet Period by Study Day in AISRS Total Score, OC
 (Efficacy Sample)

----- Analysis Visit (N)=42 -----

The TTEST Procedure

Variable: CHG (Change from Baseline)

TRTPN	N	Mean	Std Dev	Std Err	Minimum	Maximum
1	113	-10.5841	10.5117	0.9889	-40.0000	11.0000
3	123	-7.3008	10.1658	0.9166	-39.0000	12.0000
Diff (1-2)		-3.2833	10.3328	1.3464		

TRTPN	Method	Mean	95% CL Mean	Std Dev	95% CL Std Dev
1		-10.5841	-12.5434 -8.6248	10.5117	9.2969 12.0944
3		-7.3008	-9.1153 -5.4863	10.1658	9.0346 11.6234
Diff (1-2)	Pooled	-3.2833	-5.9359 -0.6306	10.3328	9.4754 11.3621
Diff (1-2)	Satterthwaite	-3.2833	-5.9399 -0.6266		

Method	Variances	DF	t Value	Pr > t
Pooled	Equal	234	-2.44	0.0155
Satterthwaite	Unequal	230.76	-2.44	0.0156

SOURCE: TTESTOC; TABLE: statli.lis; RUN: 31AUG2020 08:32; ANALYSIS DATASET CREATED: 16JUN2020 08:14
 PROGRAM: /opt/sas/Data/DAP/EB1020/P40520100014/STAT/Program.dev/DOC_STAT/stat1.sas
 OPDC, NEW DRUG APPLICATION, IND # 119,361 CENTANAFADINE STAT-4.7 FINAL

CENTANAFADINE
 PROTOCOL 405-201-00014

12 OF 24

STAT-4.7
 Unadjusted Mean Change from Baseline to Double Blind Tretmnet Period by Study Day in AISRS Total Score, OC
 (Efficacy Sample)

 ----- Analysis Visit (N)=42 -----

The TTEST Procedure

Variable: CHG (Change from Baseline)

Equality of Variances

Method	Num DF	Den DF	F Value	Pr > F
Folded F	112	122	1.07	0.7162

SOURCE: TTESTOC; TABLE: statli.lis; RUN: 31AUG2020 08:32; ANALYSIS DATASET CREATED: 16JUN2020 08:14
 PROGRAM: /opt/sas/Data/DAP/EB1020/P40520100014/STAT/Program.dev/DOC_STAT/stat1.sas
 OPDC, NEW DRUG APPLICATION, IND # 119,361 CENTANAFADINE STAT-4.7 FINAL

CENTANAFADINE
 PROTOCOL 405-201-00014

13 OF 24

STAT-4.7
 Unadjusted Mean Change from Baseline to Double Blind Tretmet Period by Study Day in AISRS Total Score, OC
 (Efficacy Sample)

 ----- Analysis Visit (N)=7 -----

The TTEST Procedure

Variable: CHG (Change from Baseline)

TRTPN	N	Mean	Std Dev	Std Err	Minimum	Maximum
2	139	-5.4460	6.6389	0.5631	-24.0000	9.0000
3	139	-3.5612	6.6693	0.5657	-31.0000	10.0000
Diff (1-2)		-1.8849	6.6541	0.7982		

TRTPN	Method	Mean	95% CL Mean	Std Dev	95% CL Std Dev
2		-5.4460	-6.5595 -4.3326	6.6389	5.9395 7.5264
3		-3.5612	-4.6797 -2.4426	6.6693	5.9667 7.5609

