 Unadjusted Mean Change from Baseline to Double Blind Tretmnet Period by Study Day in AISRS Total Score, OC
 (Efficacy Sample)

 ----- Analysis Visit (N)=35 -----

The TTEST Procedure

Variable: CHG (Change from Baseline)

Equality of Variances

Method	Num DF	Den DF	F Value	Pr > F
Folded F	103	124	1.32	0.1375

SOURCE: TTESTOC; TABLE: statli.lis; RUN: 31AUG2020 08:32; ANALYSIS DATASET CREATED: 16JUN2020 08:14
 PROGRAM: /opt/sas/Data/DAP/EB1020/P40520100014/STAT/Program.dev/DOC_STAT/stat1.sas
 OPDC, NEW DRUG APPLICATION, IND # 119,361 CENTANAFADINE STAT-4.7 FINAL

CENTANAFADINE
 PROTOCOL 405-201-00014

23 OF 24

STAT-4.7
 Unadjusted Mean Change from Baseline to Double Blind Tretmet Period by Study Day in AISRS Total Score, OC
 (Efficacy Sample)

 ----- Analysis Visit (N)=42 -----

The TTEST Procedure

Variable: CHG (Change from Baseline)

TRTPN	N	Mean	Std Dev	Std Err	Minimum	Maximum
2	102	-11.5490	11.6293	1.1515	-41.0000	11.0000
3	123	-7.3008	10.1658	0.9166	-39.0000	12.0000
Diff (1-2)		-4.2482	10.8531	1.4534		

TRTPN	Method	Mean	95% CL Mean	Std Dev	95% CL Std Dev
2		-11.5490	-13.8332 -9.2648	11.6293	10.2229 13.4878
3		-7.3008	-9.1153 -5.4863	10.1658	9.0346 11.6234
Diff (1-2)	Pooled	-4.2482	-7.1124 -1.3840	10.8531	9.9325 11.9632
Diff (1-2)	Satterthwaite	-4.2482	-7.1502 -1.3463		

Method	Variances	DF	t Value	Pr > t
Pooled	Equal	223	-2.92	0.0038
Satterthwaite	Unequal	202.31	-2.89	0.0043

SOURCE: TTESTOC; TABLE: statli.lis; RUN: 31AUG2020 08:32; ANALYSIS DATASET CREATED: 16JUN2020 08:14
 PROGRAM: /opt/sas/Data/DAP/EB1020/P40520100014/STAT/Program.dev/DOC_STAT/stat1.sas
 OPDC, NEW DRUG APPLICATION, IND # 119,361 CENTANAFADINE STAT-4.7 FINAL

CENTANAFADINE
 PROTOCOL 405-201-00014

24 OF 24

STAT-4.7
 Unadjusted Mean Change from Baseline to Double Blind Tretmnet Period by Study Day in AISRS Total Score, OC
 (Efficacy Sample)

 ----- Analysis Visit (N)=42 -----

The TTEST Procedure

Variable: CHG (Change from Baseline)

Equality of Variances

Method	Num DF	Den DF	F Value	Pr > F
Folded F	101	122	1.31	0.1554

SOURCE: TTESTOC; TABLE: statli.lis; RUN: 31AUG2020 08:32; ANALYSIS DATASET CREATED: 16JUN2020 08:14
 PROGRAM: /opt/sas/Data/DAP/EB1020/P40520100014/STAT/Program.dev/DOC_STAT/stat1.sas
 OPDC, NEW DRUG APPLICATION, IND # 119,361 CENTANAFADINE STAT-4.7 FINAL

CENTANAFADINE
PROTOCOL 405-201-00014

1 OF 6

STAT-4.8

Non-Parametric Stratified by Center Analysis of Mean Change from Baseline to Double Blind Tretmnet Period by Study Day in AISRS Total Score, LOCF

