 Variable: RESID (Residual)
 AVISITN = 42
 AVISIT = DAY 42

Moments

N	338	Sum Weights	338
Mean	0.21994106	Sum Observations	74.3400787
Std Deviation	10.206485	Variance	104.172337
Skewness	-0.4662637	Kurtosis	-0.2816581
Uncorrected SS	35122.428	Corrected SS	35106.0776
Coef Variation	4640.5546	Std Error Mean	0.5551596

Basic Statistical Measures

Location		Variability	
Mean	0.219941	Std Deviation	10.20649
Median	2.116541	Variance	104.17234
Mode	7.859023	Range	51.41794
		Interquartile Range	14.95136

Tests for Location: Mu0=0

Test	-Statistic-	-----p Value-----
Student's t	t 0.396176	Pr > t 0.6922
Sign	M 21	Pr >= M 0.0256
Signed Rank	S 1936.5	Pr >= S 0.2821

SOURCE: MMRMDX1; TABLE: statlk.lis; RUN: 31AUG2020 08:32; ANALYSIS DATASET CREATED: 16JUN2020 08:14
 PROGRAM: /opt/sas/Data/DAP/EB1020/P40520100014/STAT/Program.dev/DOC_STAT/stat1.sas
 OPDC, NEW DRUG APPLICATION, IND # 119,361 CENTANAFADINE STAT-4.9 FINAL

CENTANAFADINE
 PROTOCOL 405-201-00014

2 OF 11

STAT-4.9
 Residual at Day 42 from Proc Mixed for Change from Baseline in AISRS Total Score, Primary Efficacy Analysis Model
 (Efficacy Sample)

 The UNIVARIATE Procedure
 Variable: RESID (Residual)
 AVISITN = 42
 AVISIT = DAY 42

Quantiles (Definition 5)

Level	Quantile
100% Max	21.91943
99%	20.45404
95%	14.85949
90%	12.11174
75% Q3	7.82680
50% Median	2.11654
25% Q1	-7.12456
10%	-14.10923
5%	-18.33244
1%	-27.07807
0% Min	-29.49851

Extreme Observations

-----Lowest-----		-----Highest-----	
Value	Obs	Value	Obs
-29.4985	961	19.4617	1608
-27.6116	257	20.4540	298
-27.3096	1412	20.7976	1491
-27.0781	401	21.6142	973

SOURCE: MMRMDX1; TABLE: statlk.lis; RUN: 31AUG2020 08:32; ANALYSIS DATASET CREATED: 16JUN2020 08:14
 PROGRAM: /opt/sas/Data/DAP/EB1020/P40520100014/STAT/Program.dev/DOC_STAT/stat1.sas
 OPDC, NEW DRUG APPLICATION, IND # 119,361 CENTANAFADINE STAT-4.9 FINAL

CENTANAFADINE
 PROTOCOL 405-201-00014

3 OF 11

STAT-4.9
 Residual at Day 42 from Proc Mixed for Change from Baseline in AISRS Total Score, Primary Efficacy Analysis Model
 (Efficacy Sample)

 The UNIVARIATE Procedure
 Variable: RESID (Residual)
 AVISITN = 42
 AVISIT = DAY 42

Extreme Observations

-----Lowest-----		-----Highest-----	
Value	Obs	Value	Obs
-25.9557	1117	21.9194	1066

[figure not shown]
SOURCE: MMRMDX1; TABLE: statlk.lis; RUN: 31AUG2020 08:32; ANALYSIS DATASET CREATED: 16JUN2020 08:14
 PROGRAM: /opt/sas/Data/DAP/EB1020/P40520100014/STAT/Program.dev/DOC_STAT/stat1.sas

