 PROGRAM: /opt/sas/Data/DAP/EB1020/P40520100014/STAT/Program.dev/DOC_STAT/stat1.sas
 OPDC, NEW DRUG APPLICATION, IND # 119,361 CENTANAFADINE STAT-5.1 FINAL

CENTANAFADINE
 PROTOCOL 405-201-00014

14 OF 14

STAT-5.1
 Proc Mixed Output for Change from Baseline in CGI-S Scale, MMRM (UN)
 (Efficacy Sample)

 ----- Parameter Code=CGI0201 -----

The Mixed Procedure
 Tests of Effect Slices

Effect	Analysis Visit (N)	Num DF	Den DF	F Value	Pr > F
AVISITN*TRTPN	7	2	380	0.24	0.7878
AVISITN*TRTPN	14	2	381	2.39	0.0931
AVISITN*TRTPN	21	2	374	3.30	0.0379
AVISITN*TRTPN	28	2	370	4.03	0.0186
AVISITN*TRTPN	35	2	372	4.73	0.0094
AVISITN*TRTPN	42	2	372	4.24	0.0150

SOURCE: MMRMOUT; TABLE: statlcgisa.lis; RUN: 31AUG2020 08:32; ANALYSIS DATASET CREATED: 16JUN2020 08:14
 PROGRAM: /opt/sas/Data/DAP/EB1020/P40520100014/STAT/Program.dev/DOC_STAT/stat1.sas
 OPDC, NEW DRUG APPLICATION, IND # 119,361 CENTANAFADINE STAT-5.1 FINAL

CENTANAFADINE
PROTOCOL 405-201-00014

1 OF 6

STAT-5.2
Proc GLM Output for Change from Baseline to Day 42 in CGI-S Scale, LOCF
(Efficacy Sample)

----- Parameter Code=CGI0201 Analysis Visit (N)=42 -----

The GLM Procedure
Class Level Information

Class	Levels	Values
TRTPN	3	1 2 3
POOLCNTR	39	

Number of Observations Read 421
Number of Observations Used 421

SOURCE: GLMOUT; TABLE: stat1cgisb.lis; RUN: 31AUG2020 08:32; ANALYSIS DATASET CREATED: 16JUN2020 08:14
PROGRAM: /opt/sas/Data/DAP/EB1020/P40520100014/STAT/Program.dev/DOC_STAT/stat1.sas
OPDC, NEW DRUG APPLICATION, IND # 119,361 CENTANAFADINE STAT-5.2 FINAL

CENTANAFADINE
 PROTOCOL 405-201-00014

2 OF 6

STAT-5.2
 Proc GLM Output for Change from Baseline to Day 42 in CGI-S Scale, LOCF
 (Efficacy Sample)

 ----- Parameter Code=CGI0201 Analysis Visit (N)=42 -----

The GLM Procedure

Dependent Variable: CHG Change from Baseline

Source	DF	Sum of Squares	Mean Square	F Value	Pr > F
Model	41	75.2669725	1.8357798	1.97	0.0006
Error	379	352.9087994	0.9311578		
Corrected Total	420	428.1757720			

R-Square Coeff Var Root MSE CHG Mean
 0.175785 -118.7866 0.964965 -0.812352

Source	DF	Type III SS	Mean Square	F Value	Pr > F
TRTPN	2	6.97064551	3.48532275	3.74	0.0246
POOLCNTR	38	46.93646590	1.23517016	1.33	0.0997
BASE	1	17.18753428	17.18753428	18.46	<.0001

SOURCE: GLMOUT; TABLE: stat1cgisb.lis; RUN: 31AUG2020 08:32; ANALYSIS DATASET CREATED: 16JUN2020 08:14
 PROGRAM: /opt/sas/Data/DAP/EB1020/P40520100014/STAT/Program.dev/DOC_STAT/stat1.sas
 OPDC, NEW DRUG APPLICATION, IND # 119,361 CENTANAFADINE STAT-5.2 FINAL

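### Two ANCOVA tables labelled OC (STAT-4.3 for AISRS, STAT-5.3 for CGI-S) were run on the LOCF data and give no observed-case result

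*SAP*

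**What the plan says.** SAP section 5.2 describes the OC data set as holding only values actually recorded at each double-blind visit, with nothing imputed. It plans an ANCOVA on OC data for AISRS total score and for every continuous change-from-baseline efficacy endpoint, alongside the LOCF ANCOVA. Section 8.1.3.1 gives the models under the sensitivity analyses for the missing-at-random assumption: baseline and treatment in both, with study center in the LOCF model and not in the OC model.

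The statistical documentation supplied with the SAP prints these analyses in pairs. For AISRS, STAT-4.2 is titled "Proc GLM Output for Change from Baseline to Day 42 in AISRS Total Score, LOCF" and STAT-4.3 is titled "Proc GLM Output for Change from Baseline to Day 42 in AISRS Total Score, OC". For CGI-S, STAT-5.2 is titled "Proc GLM Output for Change from Baseline to Day 42 in CGI-S Scale, LOCF" and STAT-5.3 carries the matching OC title.

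**The concern.** An OC table at Day 42 should contain fewer subjects than its LOCF partner whenever anyone has no Day 42 value. Both OC tables instead contain all 421 subjects of the Efficacy Sample. If they hold carried-forward values, two printed sensitivity results are wrong under the SAP's own definition, and a reader who takes the LOCF and OC tables as two views of the missing data is comparing one data set with itself.

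The risk of misreading is greatest for CGI-S at 400 mg. The LOCF table gives p=0.0437 and the table labelled OC gives p=0.0668, which would be read as the key secondary effect weakening on observed data.

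**Working it through.** **Inputs.** Treatment codes 1, 2 and 3 are 200 mg, 400 mg and placebo (the baseline means match STAT-1.1).

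| Day 42 AISRS change | 200 mg: n, mean, SD | 400 mg: n, mean, SD | Placebo: n, mean, SD |
|---|---|---|---|
| STAT-4.2 (LOCF) and STAT-4.3 (labelled OC), identical | 140, -10.7071, 10.8359 | 140, -11.0571, 10.7126 | 141, -7.1348, 10.1624 |
| STAT-4.7 (OC t-tests) | 113, -10.5841, 10.5117 | 102, -11.5490, 11.6293 | 123, -7.3008, 10.1658 |

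**Step 1: reproduce the printed STAT-4.3.** Total SS = Σ(n-1)SD² + Σn(mean - grand mean)². With the 140/140/141 figures this is 46730.98 + 1325.48 = 48056.45, as printed in both STAT-4.2 and STAT-4.3. Error SS = within-arm SS - baseline SS = 46730.975 - 618.365 = 46112.610, as printed in STAT-4.3.

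**Step 2: link the two tables.** If STAT-4.3 is STAT-4.2 without center on the same data, its error SS must equal the STAT-4.2 error SS plus the Type III center SS: 39250.456 + 6862.154 = 46112.610. It does.

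**Step 3: what OC data would give.** The STAT-4.7 figures give N = 113 + 102 + 123 = 338 and total SS = 38642.74 + 1144.92 = 39787.66, which matches neither table.

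**Step 4: confirm 338.** STAT-4.9, "Residual at Day 42 from Proc Mixed for Change from Baseline in AISRS Total Score, Primary Efficacy Analysis Model", has N=338 at Day 42. Observed records by visit sum to 415 + 389 + 375 + 366 + 344 + 338 = 2227, the record count of the primary MMRM.

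**Step 5: carried-forward values.** 421 - 338 = 83 (19.7%). By arm:

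- 200 mg: 140 - 113 = 27 (19%)
- 400 mg: 140 - 102 = 38 (27%)
- placebo: 141 - 123 = 18 (13%)

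**Step 6: CGI-S.** STAT-5.2 and STAT-5.3 share arm Ns, means and SDs. The rebuilt total SS is 420.6066 + 7.5692 = 428.1758, as printed in both. The link in Step 2 holds again: 352.9088 + 46.9365 = 399.8453, the STAT-5.3 error SS. No Day 42 CGI-S count is printed. The CGI-S MMRM used 2220 records, 7 fewer than AISRS, on the same double-blind visit schedule. With 421 observed at Day 42, the other five visits would average (2220 - 421)/5 = 359.8, against (2227 - 338)/5 = 377.8 for AISRS, which is not credible. Assuming CGI-S was rated only where AISRS was, 331 to 338 were observed and 83 to 90 (20 to 21%) are carried forward.

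**Step 7: size, like for like.** Pooled t-tests on the two rows of the table reproduce STAT-4.6 and STAT-4.7:

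| Versus placebo | LOCF, unadjusted | OC, unadjusted | Printed as OC in STAT-4.3 |
|---|---|---|---|
| 200 mg | -3.572 (SE 1.253, p=0.0047) | -3.283 (SE 1.346, p=0.0155) | -3.583 (p=0.0045) |
| 400 mg | -3.922 (SE 1.246, p=0.0018) | -4.248 (SE 1.453, p=0.0038) | -3.719 (p=0.0033) |

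Moving from LOCF to OC weakens the 200 mg estimate by 0.29 and strengthens the 400 mg estimate by 0.33.

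**Step 8: baseline-adjusted OC estimates.** These cannot be computed, because baselines of the 338 are not printed. For a range, assume the OC baseline difference from placebo is within ±1.5 points (an assumption without a source in the documents). The STAT-4.3 slope is (-3.9224 + 3.7189)/1.1189 = -0.182, which gives -3.01 to -3.56 at 200 mg and -3.98 to -4.52 at 400 mg. The Day 42 baseline slope in the primary MMRM (STAT-4.1.1) is -0.2232; 0.2232 × 1.5 = 0.335 gives -2.95 to -3.62 and -3.91 to -4.58.

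**The case against.** The strongest reply is that this is an output error and not a fault in the plan. The SAP's OC definition and model are sound, and the output was run on 31 August 2020, after the SAP was signed on 26 May 2020. That stands, and it is why no SAP change is proposed.

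Next, the summary tables that the SAP lists for OC change from baseline are CT-5.2.6.2 and CT-5.4.3 (section 13). They are given by title only and may be correct. That also stands: the documents show two wrong tables, not that the planned OC ANCOVA is missing everywhere.

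Third, observed-data results exist for both endpoints, because the MMRM runs on OC data: at Day 42, AISRS p=0.0021 and 0.0009, CGI-S p=0.0073 and 0.0245 (200 mg and 400 mg). The SAP also plans delta-adjusted, placebo-based and model-based sensitivity analyses. This limits the harm but does not make the two tables right.

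Two supporting points are weak. The STAT-4.3 footer, "SOURCE: GLMOUT; TABLE: stat1c.lis", shares its source name with the LOCF table, while the OC t-tests have their own, "SOURCE: TTESTOC; TABLE: statli.lis". But GLMOUT also covers CGI-S and may only name a program module, so it hints at where to look and proves nothing. The adjusted range in Step 8 depends on the slope: with the MMRM slope, the 200 mg range just includes the printed -3.58. The finding rests on the numerical identity and needs neither point.

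**Conclusion.** The concern holds. STAT-4.3 and STAT-5.3 are the LOCF ANCOVAs with center removed, under an OC label. For AISRS this follows directly from the printed output: 83 of 421 values are carried forward, at twice the rate on 400 mg (27%) as on placebo (13%). For CGI-S the identity with LOCF is exact; only the count of 83 to 90 rests on the assumption in Step 6.

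The mislabelled AISRS table shows the two doses nearly equal, whereas the unadjusted OC differences are about one point apart (4.248 - 3.283 = 0.965). Both remain below 0.05. For CGI-S no OC contrast outside the MMRM is printed, so the planned OC ANCOVA result is unknown, and the move from p=0.0437 to p=0.0668 reflects only the loss of the center term. The primary and key secondary MMRMs and the fixed-sequence tests are untouched. The tables should be corrected, but no confirmatory conclusion depends on them.

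**What to change.** Rerun STAT-4.3 and STAT-5.3 on the OC data set with the prespecified model (treatment and baseline, no center). The AISRS table should then show N=338 (113/102/123) and a corrected total SS near 39787.7 on 337 df; for CGI-S, check the Ns against the observed Day 42 ratings. Check the Ns in CT-5.2.6.2, CT-5.4.3 and the other OC ANCOVA tables for the same error. Leave the SAP model as it is. A center-adjusted OC ANCOVA may be added if labelled post hoc.

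The cost is one input correction, two reruns and a check of Ns, with no SAP amendment and no effect on the confirmatory tests.
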